8.4 Study design

This is a multi-center, double-blind, randomized, placebo-controlled multiple ascending dose trial in post-menopausal women with vasomotor symptoms.

Subjects will be recruited into a maximum of 5 sequentially dosed cohorts; Cohort 1 (50 mg NT-814), Cohort 2 (100 mg NT-814), Cohort 3 (150 mg NT-814) and, if needed, 2 further cohorts up to 400mg NT-814. See [Figure 1](#) for study design schematic.

For each cohort, subjects will enter a 4 week screening period to determine eligibility. Twenty eligible subjects will be randomized per cohort (15 active and 5 placebo).

During the screening period each subject will be required to complete twice daily paper diaries. Eligible subjects will demonstrate, at the Baseline visit, an average 24-hour moderate to severe hot flash frequency ≥ 7 and ≤ 20 based upon the average daily frequency of all available readings (at least 4 days) in the final week of screening (Week -1). If at the Baseline visit subjects have an average 24-hour hot flash frequency < 7 /day or > 20 /day they will be discontinued from the study. In addition, subjects that have a change of $\geq 50\%$ in average 24-hour hot flash frequency between the first and second week of the screening period (Week -2 and Week -1 respectively) will be excluded. Subjects will also be provided with the continuous daily diary during screening and instructed to start completing this on the morning of Day -1 after waking, prior to admission to the clinic, and to continue to complete this throughout Day -1.

It may be necessary to extend a patient's screening period beyond 28 days (with the approval of the sponsor) when a subject is held over from one cohort to the next because the original cohort into which they would have been enrolled is complete. If this occurs, the following safety procedures must be repeated such that the most recent evaluation occurs within 28 days of the rescheduled randomization:

- Biochemistry and hematology
- Vital signs
- 12-lead ECG
- Physical examination

If the subject has completed (or partially completed) the screening twice daily Hot Flash Diary this must still be repeated and a new diary started on the new planned Day -15 and completed for the 2 weeks up to Day -2. Eligibility will be assessed on the repeated diary, not the initial one. If the subject had not started completing their screening diary at the time screening was put on hold, they will start this screening diary on the re-scheduled Day -15.

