8.2 Handling of Dropouts or Missing Data

For the calculation of the luteinizing hormone AUC_{0-8} at any visit,

- If more than one time point is missing, then the AUC won't be calculated and will be considered as missing.
- If one of the following time points is missing (T1, T2, T3, T4, T5, T6, T7) then the AUC will be calculated without the missing time point.
- If one of the following time points is missing (T0 or T8), then the AUC won't be calculated and will be considered as missing.

For the derivation of the daily scores in the efficacy section, the daily derivation will not be calculated and will be treated as missing if the results of the corresponding day are incomplete:

Twice daily diary

- The hot flash data are collected twice (day time and night time) and if either period is not complete, then the whole day will be considered incomplete and therefore missing for the corresponding daily variable derived. For each period of the diary to be considered incomplete, there must be no hot flashes of any severity recorded and the box indicating that there were no hot flashes must also not have been completed.

Continuous diary

- For the hot flash data, the diary will be considered incomplete if there are no hot flashes of any severity recorded and the box indicating that there were no hot flashes has also not been completed.
- For NTA not associated with hot flashes, the diary will always be considered complete

Skin Conductance

- If the skin conductance device has not recorded the hot flashes for a continuous period (e.g. due to battery failure) on a given day, then the whole day is considered incomplete and therefore missing for the corresponding daily variable derived.

For the calculation of the weekly scores, at least 4 complete days are needed for the derivations of the weekly values. The results from the complete days will then be averaged to give the weekly score.

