8.10.2 Continuous Hot Flash Diary

8.10.2.1 Frequency of Hot Flashes

Frequency by day

Daily (24-hour) frequency of hot flashes for Day Y for the continuous hot flash diary will be equal to the number of hot flashes recorded on Day Y (day period + night period)

The daily frequency of mild, moderate, severe, moderate/severe, and total hot flashes as measured by continuous day-time diary will be summarized for each day. The mean (+SE) in frequency of mild, moderate, severe, moderate/severe, and total hot flashes will be displayed graphically by day. The change from Day -1 will also be summarized.

Average daily frequency by week

The average daily frequency of hot flashes for Week 1 will be equal to the average of the daily frequency of hot flashes from Day 1 to Day 7, inclusive.

The Week 1 average frequency of mild, moderate, severe, moderate to severe, and total hot flashes will be summarized by treatment.

Statistical analysis

The analysis will test the treatment difference of daily frequency of moderate/severe hot flashes from Day -1 to Day 7 and Day 14.

The analysis will be based on a linear mixed-effects model with the change from Day -1 as a dependent variable, treatment, day and treatment-by-day interaction as fixed effects, subject as a random effect, and the number of moderate/severe hot flashes at Day -1 and the interaction with day as covariates. Subjects dosed with placebo will be analyzed as a pooled group. An unstructured covariance matrix will be specified for the repeated measures at postdose timepoints for each subject. From this analysis, the LS mean and 2-sided 90 % CIs will be calculated for the contrast “NT-814 versus placebo” at each treatment and each postdose day, separately.

Following is the SAS code for reference:

```
proc mixed data=dataset ;  
class TRT <50 mg NT-814, 100 mg NT-814, 150 mg NT-814, etc..., placebo> DAY <7,14> USUBJID;  
model CHG = TRT DAY TRT*DAY BSL BSL*DAY / s ddfm=kr;  
random USUBJID;  
repeated DAY / type=un subject=USUBJID;  
lsmeans TRT*DAY / cl diff alpha=0.1;  
run;
```

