8.10.2.2 Night Time Awakenings

8.10.2.2.1 Night Time Awakenings Secondary to Hot Flashes

Night time awakenings secondary to hot flashes for Day Y = the sum of the number of moderate and severe night time hot flashes recorded on the continuous diary (as these are defined as resulting in a night time awakening) .

Frequency by day

The NTA secondary to hot flashes will be summarized for each day and displayed graphically by day. The change from Day -1 will also be summarized.

Average daily frequency by week

The average daily NTA secondary to hot flashes for Week 1 will be equal to the average of the NTA from Day 1 to Day 7. The average daily NTA secondary to hot flashes for Week 1 will be summarized by treatment.

The same statistical analyses for the daily scores as described in section 8.10.2.1 will be done based on the change from Day -1 NTA.

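### SAP 8.2 tests the continuous diary for completeness once per day, so an unrecorded night passes as complete and is scored as zero flashes and zero awakenings

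*SAP*

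**What the plan says.** SAP 8.2 makes a derived daily value missing only through the completeness test: it "will be treated as missing if the results of the corresponding day are incomplete". The test differs between the two diaries.

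- **Twice-daily diary.** Day and night are checked separately, each with its own entries and no-flash box: "if either period is not complete, then the whole day will be considered incomplete and therefore missing".
- **Continuous diary.** There is one check, with two conditions that must both hold. The first reads: "For the hot flash data, the diary will be considered incomplete if there are no hot flashes of any severity recorded". The second is an unticked no-flash box. Day and night periods are not mentioned.
- **Awakenings without a flash, continuous diary.** "For NTA not associated with hot flashes, the diary will always be considered complete".

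The derivations then use whatever was recorded. SAP 8.10.2.1 makes the 24-hour frequency "equal to the number of hot flashes recorded on Day Y (day period + night period"), with no adjustment for the time covered. SAP 8.10.2.2.1 takes awakenings secondary to flashes as "the sum of the number of moderate and severe night time hot flashes recorded on the continuous diary". The next section adds awakenings without a flash to give total awakenings.

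The model in SAP 8.10.2.1 analyses the change from Day -1 to Days 7 and 14, with Day -1 also a covariate. Awakenings secondary to flashes use the same model. The SAP table list includes a statistical analysis of total awakenings (Table 14.2.2.3.3). Week 1 averages are summarised.

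**The concern.** The continuous diary's daily value is a day count plus a night count, as for the twice-daily diary, but only the twice-daily diary must have both parts present. A woman who records by day and leaves the night blank has a complete day. Her night adds nothing to the frequency, and both awakening variables are zero, the best possible score.

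Such a night never reaches the mixed model as a missing value. It enters as an observed zero, so the model's handling of missing data cannot help. The values at risk are single days: one baseline day and two modelled days per subject, with no averaging to dilute an undercount. The Week 1 averages are also exposed, because the requirement of at least 4 complete days uses the same definition of complete.

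Protocol 11.3 leaves the rules for incomplete diary entries to the SAP, so SAP 8.2 is where this has to be settled.

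**Working it through.** The plan gives no figure on this point to reproduce.

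**Step 1: apply both rules to the same day.** Take daytime flashes recorded, night blank, no box ticked.

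| Recorded by day | Continuous-diary rule | Twice-daily rule |
|---|---|---|
| 7 flashes | frequency 7, awakenings 0 | missing |
| 1 flash | frequency 1, awakenings 0 | missing |

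**Step 2: how often an unrecorded night would be caught.** Inputs: 7 moderate or severe flashes a day, the entry minimum (Protocol 7.2). Assumptions not in the documents: Poisson counts, and 60% of flashes by day (range 50–70%). The rule catches the night only if no daytime flash is recorded, so P(caught) = exp(−7 × daytime share). Flashes lost = 7 × night share. The shift in the mean of a 15-subject arm from one such subject is that loss divided by 15.

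| Daytime share | P(caught) | Passes as complete | Flashes lost | Arm-mean shift |
|---|---|---|---|---|
| 50% | exp(−3.5) = 3.0% | 97.0% | 3.5 | 3.5/15 = 0.23 |
| 60% | exp(−4.2) = 1.5% | 98.5% | 2.8 | 2.8/15 = 0.19 |
| 70% | exp(−4.9) = 0.7% | 99.3% | 2.1 | 2.1/15 = 0.14 |

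Mild flashes also count toward completeness, so the true chance of being caught is, if anything, lower. At 20 a day, the entry maximum, with 40% at night, the loss is 20 × 0.4 = 8.0 flashes. At an assumed on-treatment rate of 2 a day with 60% by day, exp(−1.2) = 30% are caught. Whether an unrecorded night is excluded therefore depends on the flash rate, which is the outcome.

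**Step 3: effect on the contrast with placebo.** Assume 10% unrecorded nights in each arm, 40% of flashes at night, placebo at 7 a day and active at 3.5. Ignore the nights that are caught.

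- Placebo undercount: 0.10 × 7 × 0.4 = 0.28
- Active undercount: 0.10 × 3.5 × 0.4 = 0.14
- Difference: 0.28 − 0.14 = 0.14 a day, toward the null

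In this example the undercounts are equal when the active arm's rate of unrecorded nights is twice placebo's (0.20 × 3.5 × 0.4 = 0.28). Above that, the contrast overstates the benefit.

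**Step 4: how often a blank night is a true zero.** With the same 40% night share, P(no night flash) is exp(−2.8) = 6% at 7 a day. It is exp(−1.4) = 25% after a 50% reduction and exp(−0.7) = 50% after a 75% reduction.

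**The case against.** The strongest reply is that the continuous diary is an event log, filled in as flashes occur, while the twice-daily diary has two scheduled entries. In an event log a blank night is also what a flash-free night looks like, so different rules may be reasonable. This stands in part: a blank cannot be presumed missing. Equally, a rule that always scores it as zero cannot presume it observed.

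Second, the form is not shown. SAP 8.2 does not say whether the no-flash box is per day or per period, and it says "if" rather than "only if". A per-period reading is possible, but it is not written, and the explicit per-period wording for the other diary argues against it. The point matters for the remedy. With one box per day, copying the twice-daily rule would delete the flash-free nights in Step 4, and most often in the best responders.

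Third, the scope is narrow. Efficacy is exploratory, subjects are inpatients on most of these days, so blanks may be few, and the raw diary data are listed. SAP 3.5 names the twice-daily diary for the awakenings endpoint, so continuous-diary awakenings are supplementary. All of this stands and limits the size of the point.

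Fourth, a reader might see a conflict with the missing-at-random statement in SAP 8.2. There is none: that statement concerns values already classed as missing, and the gap lies in how they are classed.

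**Conclusion.** The point holds in a limited form. As written, any daytime flash makes a continuous-diary day complete, and an unrecorded night then enters the 24-hour frequency and both awakening variables as zero. Under the Step 2 assumptions the rule would miss about 97–99% of such nights at the entry minimum, each losing 2.1–3.5 flashes. These figures are conditional on a night being unrecorded, and the documents give no basis for that rate. The consequences are confined to the continuous-diary analyses: the Day -1 baseline, Days 7 and 14, and the Week 1 averages. The weekly twice-daily analyses are unaffected.

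The documents do not support two stronger readings.

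- **That the rule manufactures a drug effect.** A blank night after dosing flatters that subject's change, but the modelled estimate is NT-814 against placebo under double blinding. Equal rates of unrecorded nights bias it toward the null. A false benefit needs sufficiently more of them on active treatment, and nothing indicates that.
- **That a late-started Day -1 corrupts the baseline.** Subjects are "instructed to start completing this on the morning of Day -1 after waking, prior to admission to the clinic", and no analysis rule checks this. However, admission is on the morning of Day -1 (Protocol 8.4), and the conductance monitor is fitted 24 hours ± 1 hour before planned dosing (Protocol 10.2.3). Recording from admission would still cover roughly 24 hours to dosing. Day 14 has the same on-waking start, so the two days are aligned by design.

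**What to change.** In SAP 8.2, judge the day and night periods of the continuous diary separately, and state whether the no-flash box is per period or per day.

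- **One box per period:** a period with no entry and no ticked box is incomplete, and the daily frequency is missing.
- **One box per day:** a blank night counts as zero only when the twice-daily diary's entry the next morning confirms no flashes for that night. Otherwise it is missing. Protocol 10.2.1 has the twice-daily diary kept until the morning of Day 15, so this check is planned for every modelled night.
- **Awakenings:** set both continuous-diary awakening variables to missing when the night is classed as missing, and replace the statement that the diary is always complete for awakenings without a flash.

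The cost is SAP wording and programming, with no new data collection. The downside is that some subject-days become missing. Making the change before the blind is broken keeps the classification independent of treatment.

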8.3 Multicenter Studies

This is a multi-center study.

8.4 Examination of Subgroups

No pre-specified subgroup analysis is planned.

8.5 Analysis Populations

The following data sets will be used for the statistical analysis.

1. All Subjects Set: all subjects who signed the informed consent.
2. All Randomized Set: all subjects who were randomized.
3. Safety Set: all subjects who receive at least 1 dose of double-blind study drug (any dose of NT-814 or matching placebo). Subjects will be analyzed according to treatment received.
4. Full Analysis Set: all randomized subjects who received at least 1 dose of double-blind study drug and for whom the efficacy data are considered sufficient and interpretable. Subjects will be analyzed according to randomized treatment.

Analysis sets will be identified prior to the unblinding of the study data.

8.6 Subject Accountability

Summaries of analysis populations and subject disposition will be presented by treatment based on the All Randomized Set and will contain the following information:

- Number and percent of subjects who were dosed.
- Number and percent of subjects who completed the study (completed the Day 21 follow-up call)
- Number and percent of subjects who discontinued early and reason for early discontinuation
- Number and percent of subjects in the Safety and Full Analysis Set

Subject disposition will be presented in listings.

The screening outcomes will be listed and summarized based on the All Subjects Set.

The randomization allocation and the reason for exclusion from each population will also be listed.

8.7 Protocol Deviation Reporting

Protocol deviations determined to have significant or potential impact on the safety or integrity of the study data will be listed only.

8.8 Subject Demographics and Baseline Characteristics

Demographics (sex, age [in years, at time of signing informed consent], race, and ethnicity) and physical measurements (height, weight, and body mass index) will be listed and summarized by treatment based on the safety set.

8.9 Study Drug Exposure and Compliance

Duration of study drug exposure (in days) will be calculated as: last dose date – first dose date + 1 day, regardless of study drug interruption. Exposure summaries will be based on the safety set.

Dosing administration will be presented in an individual subject data listing.

8.10 Analysis of Efficacy Data

All efficacy analyses will be performed using the Full Analysis Set and are considered as exploratory. Any statistical hypothesis tests and/or CIs will be two-sided, using a type I error rate of 0.1. No adjustments will be made for multiplicity in this early phase study. An unstructured covariance matrix is planned for the analyses that use linear mixed-effects models. However, alternative covariance matrices may be used if the unstructured matrix causes model convergence issues.

8.10.1 Twice Daily Hot Flash Paper Diaries

8.10.1.1 Frequency of Hot Flashes

Frequency by day

Daily (24-hour) frequency of hot flashes for Day Y will be equal to the number of hot flashes recorded on Day Y (day time hot flushes recorded in the evening + night time hot flushes recorded the following morning).

The daily frequency of mild, moderate, severe, moderate/severe, and total hot flashes will be summarized for each day. The mean (\pm SE) frequency of mild, moderate, severe, moderate/severe (moderate and severe combined), and total hot flashes will be displayed graphically by day (Day -8 onwards).

Average daily frequency by week

The average daily frequency of hot flashes for each of Week -1, Week 1, and Week 2 will be equal to the average of the daily frequency of hot flashes from Day -8 to Day -2 inclusive, from Day 1 to Day 7 inclusive, and from Day 8 to Day 14 inclusive, respectively.

The average daily frequency by week and the change from Week -1 (for Week 1 and Week 2) of mild, moderate, severe, moderate/severe, and total hot flashes will be summarized descriptively by treatment.

Statistical analysis

The analysis will test the treatment difference of change in the average daily frequency of moderate/severe hot flashes from Week -1 to each of Week 1 and Week 2.

The analysis will be based on a linear mixed-effects model with the change from Week -1 as a dependent variable, treatment, week, treatment-by-week interaction as fixed effects, subject as a random effect, and baseline (frequency of moderate/severe hot flashes at Week -1) and baseline-by-week interaction as covariates. Subjects dosed with placebo will be analyzed as a pooled group. An unstructured covariance matrix will be specified for the repeated measures at postdose timepoints for each subject. From this analysis, the least-squares (LS) mean and 2-sided 90% CIs will be calculated for the contrast “NT-814 versus placebo” for each treatment and each postdose week, separately.

Following is the SAS code for reference:

```
proc mixed data=dataset ;  
class TRT <50 mg NT-814, 100 mg NT-814, 150 mg NT-814, etc... , placebo> WEEK <1,2> USUBJID;  
model CHG = TRT WEEK TRT*WEEK BSL BSL*WEEK / s ddfm=kr;  
random USUBJID;  
repeated WEEK / type=un subject=USUBJID;  
lsmeans TRT*WEEK / cl diff alpha=0.1;  
run;
```

The analysis assumes a constant average treatment difference on the original scale. The possibility of a proportional treatment effect will also be explored as it is not certain whether the continuous endpoints will be normally or log-normally distributed, and/or whether an absolute or proportional change in endpoints will be observed. If deemed necessary, data will be log transformed prior to the analysis. The subsequent results (mean differences and corresponding CIs) will be back transformed and hence reported in terms of ratios of geometric means.

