8.10.3 Sternal Skin Conductance Monitors

Frequency by day

The Day -1 frequency of hot flashes will be the number of hot flashes detected by the device from 24 hours before dosing on Day 1 to the dosing on Day 1. If there is >24 hours of recorded data, then only the 24-hour prior to the time of dosing on Day 1 will be used. If there is <24 hours of data recorded, then all the recorded data will be used and the actual recording duration will be used to derive a 24 hour value.

Postbaseline values will be based on 24-hour periods from the dose time on Day 1. If the recording time on Day 7 (or an earlier day in the event of early withdrawal) is <24 hours, then all the recorded data will be used and the actual recording duration will be used to derive a 24-hour value.

The number of algorithm-detected hot flashes (Bahr et al *Physiol Meas.* 2014 February ; 35(2): 95–110. doi:10.1088/0967-3334/35/2/95; algorithm commercial property of SimplexScientific LLC) will be summarized and displayed graphically for each day by treatment. The change from Day -1 will also be summarized.

Average daily frequency by week

The average daily frequency of hot flashes detected by the device for Week 1 will be equal to the average of the daily frequency of hot flashes detected by the device from Day 1 to Day 7 inclusive.

The average daily frequency for Week 1 will be summarized by treatment.

Statistical analysis

The same statistical analyses as described in Section 8.10.2.1 will be done for the change from Day -1 in the frequency of hot flashes detected by the device.

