8.10.4 Luteinizing Hormone

The observed values on Day -1, Day 1, and Day 7, and change from Day -1 (for Day 1 and Day 7) data for continuous LH AUC₀₋₈ values will be summarized by treatment at each visit. The AUC₀₋₈ will be derived using the trapezoidal method and based on the actual times.

An analysis will be based on a linear mixed-effects model with the change from Day -1 as a dependent variable, treatment, day and treatment-by-day interaction as fixed effects, subject as a random effect and the AUC₀₋₈ value at Day -1 and the interaction with day as covariates. Subjects dosed with placebo will be analyzed as a pooled group. An unstructured covariance matrix will be specified for the repeated measures at postdose timepoints for each subject. From this analysis, the LS mean and 2-sided 90 % CIs will be calculated for the contrast “NT-814 versus placebo” at each treatment and each postdose day, separately.

Following is the SAS code for reference:

```
proc mixed data=dataset ;  
class TRT <50 mg NT-814, 100 mg NT-814, 150 mg NT-814, XX mg NT-814(2 further ascending doses up to 400mg), placebo>  
DAY <1,7> USUBJID;  
model CHG = TRT DAY TRT*DAY BSL BSL*DAY / s ddfm=kr;  
random USUBJID;  
repeated DAY / type=un subject=USUBJID;  
lsmeans TRT*DAY / cl diff alpha=0.1;  
run;
```

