The analysis for QTcF will be based on a linear mixed-effects model with change-from-baseline QTcF (Δ QTcF) as the dependent variable, time (categorical), treatment (each NT-814 dose group and all placebo group), and time-by-treatment interaction as fixed effects, and baseline QTcF as a covariate. Baseline will be the derived QTc intervals from the ECG timepoint recorded predose on Day 1. Subjects dosed with placebo will be analyzed as a pooled group. An unstructured covariance matrix will be specified for the repeated measures at postdose timepoints for each subject. If the model with unstructured covariance matrix fails to converge, other covariance matrix such as autoregressive and compound symmetry will be considered. From this analysis, the LS mean and 2-sided 90 % CIs will be calculated for the contrast “NT-814 versus placebo” at each treatment and each postdose timepoint, separately. These analyses will be performed using the QT/QTc population.

For HR, PR, QTcB, QT, RR, and QRS intervals, the analysis will be based on the change-from-baseline post-dosing (Δ HR, Δ PR, Δ QTcB, Δ QT, Δ RR, and Δ QRS). The same model will be used as described for QTcF. The LS mean, SE and 2-sided 90% CI from the statistical modeling for both change-from-baseline and placebo-corrected change-from-baseline values will be listed in the tables and graphically displayed.

Categorical Analyses

The analyses results for categorical outliers, T-wave morphology and U-wave presence will be summarized in frequency tables with counts percentages for both number of subjects and number of timepoints. For categorical outliers, the number (percentage) of subjects as well as timepoints who had increases in absolute QTc (QTcF and QTcB) values >450, 480, and 500 msec, and changes from predose baseline of >30 or >60 msec; increase in PR from predose baseline >25% to a PR >200 msec; increase in QRS from predose baseline >25% to a QRS >120 msec; decrease in HR from predose baseline >25% to a HR <50 bpm; and increase in HR from predose baseline >25% to a HR >100 bpm will be determined. For T-wave morphology and U-wave presence, the analyses will be focused on change from baseline (i.e., treatment-emergent changes). These analyses will be performed using the QT/QTc population.

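### Does the random subject effect alongside an unstructured covariance over two timepoints harm the efficacy and LH models?

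*SAP*

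**What the plan says.** Three SAP sections define a mixed model for change from baseline. All include treatment, timepoint, their interaction, baseline and baseline-by-timepoint.

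- 8.10.1.1 (twice-daily diary, Weeks 1 and 2): "subject as a random effect, and baseline (frequency of moderate/severe hot flashes at Week -1", with "repeated WEEK / type=un subject=USUBJID" in the code.
- 8.10.2.1 (continuous diary, Days 7 and 14): "subject as a random effect, and the number of moderate/severe hot flashes at Day -1 and the interaction with day as covariates", again with an unstructured matrix.
- 8.10.4 (LH AUC, Days 1 and 7): "subject as a random effect and the AUC₀₋₈ value at Day -1 and the interaction with day as covariates", again with an unstructured matrix.

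Each code block has a `RANDOM` statement for subject as well as the `REPEATED` statement, and uses Kenward-Roger degrees of freedom. Sections 8.10.1.2 to 8.10.1.4 reuse the first model. Section 8.10.2.2 reuses the second for awakenings due to hot flashes. Section 8.10.3 also reuses the second: "The same statistical analyses as described in Section 8.10.2.1 will be done for the change from Day -1".

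On fallback, the introduction to 8.10 says that "alternative covariance matrices may be used if the unstructured matrix causes model convergence issues". The by-timepoint QTcF model in 8.11.7 differs. Its terms end with "and time-by-treatment interaction as fixed effects, and baseline QTcF as a covariate", with no random subject effect, and it adds: "If the model with unstructured covariance matrix fails to converge, other covariance matrix such as autoregressive and compound symmetry will be considered".

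**The concern.** An unstructured matrix over two timepoints already carries all the within-subject correlation the data can show. A random intercept on top of it adds a parameter that the data cannot separate from the residual covariance. The information matrix for the covariance parameters is then singular, and a fitting program may respond with a warning or a convergence failure.

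The only remedy that 8.10 offers for convergence trouble is to replace the unstructured matrix, and it names no replacement. An analyst could therefore blame the wrong term and choose a simpler structure after seeing the data. If that structure assumes equal variances and the true variances differ, the confidence intervals would change. The QTcF model in the same SAP avoids the redundancy and gives examples of alternatives, which makes 8.10 look careless by comparison.

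**Working it through.** **Inputs.** From SAP 8.10.1.1, 8.10.2.1 and 8.10.4: two post-dose levels per model, one random subject variance, an unstructured residual matrix, the fixed effects and Kenward-Roger df. From SAP 4.1 and 8.10: 15 active and 5 placebo subjects per cohort, placebo pooled, two-sided alpha 0.1. The documents state no variances and no result to reproduce. The numerical check therefore assumes a post-dose covariance of [[9, 7], [7, 16]] and about 8% of subjects missing the second timepoint.

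**1. Parameter count.** An unstructured 2x2 matrix R has 2 x 3 / 2 = 3 elements. The subject variance s makes 4. The covariance of a subject's two records is V = sJ + R (J is all ones), that is

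V11 = s + r11, V12 = s + r12, V22 = s + r22.

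Adding d to s and subtracting d from every element of R leaves V as it was. The map from 4 parameters to 3 elements has rank 3, so s is not identifiable but V is. Because s = 0 is allowed, the set of possible V is the same as for the unstructured matrix alone.

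**2. What the results depend on.** The REML criterion, the estimate (X'V⁻¹X)⁻¹X'V⁻¹y and its model-based variance (X'V⁻¹X)⁻¹ are functions of V only. V is linear in the parameters, so the Kenward-Roger adjustment is the same for any generalised inverse of the singular information matrix.

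**3. Numerical check, 80 subjects (4 cohorts).** Three starting values gave three different splits of the same V:

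| s | r11 | r12 | r22 | s + r11 | s + r12 | s + r22 | -2 REML |
|---|---|---|---|---|---|---|---|
| 0.987 | 5.358 | 5.033 | 15.368 | 6.345 | 6.020 | 16.355 | 480.7916 |
| 6.291 | 0.054 | -0.271 | 10.065 | 6.345 | 6.020 | 16.356 | 480.7916 |
| 3.874 | 2.472 | 2.147 | 12.482 | 6.346 | 6.021 | 16.356 | 480.7916 |

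The unstructured matrix alone gave V = (6.3453, 6.0203, 16.3554) and the same criterion. The information matrix had rank 3 of 4 with the random effect and 3 of 3 without it.

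Top dose versus placebo, identical with and without the random effect:

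| Subjects | Timepoint | Estimate | SE | Kenward-Roger SE | df |
|---|---|---|---|---|---|
| 80 | Week 1 | -4.341 | 0.8610 | 0.8610 | 74.0 |
| 80 | Week 2 | -4.773 | 1.4108 | 1.4117 | 70.5 |
| 100 | Week 1 | -2.397 | 0.9897 | 0.9897 | 93.0 |
| 100 | Week 2 | -4.065 | 1.2904 | 1.2910 | 88.7 |

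The Week 1 df agree with a direct count: 80 - 6 = 74 (five group means and one baseline slope), and 100 - 7 = 93 with a sixth group.

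**4. The fallback, if it were used.** With complete data and r the ratio of the second SD to the first, homogeneous compound symmetry multiplies the standard error by sqrt((1 + r²)/2) at the first timepoint, and by that value divided by r at the second.

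- r = 1: both factors are 1, so no change.
- r = 1.25: sqrt(2.5625/2) = 1.132 and 1.132/1.25 = 0.906, that is +13.2% and -9.4%.

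Heterogeneous compound symmetry has two variances and one correlation. At two timepoints that is the unstructured matrix in another form, so nothing changes.

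**The case for a change.** The strongest case for a change is that the redundancy is certain, appears in prose as well as code, and runs through most of the efficacy tables. A singular information matrix is a plausible source of a warning, and 8.10 would then point the analyst at the wrong term. Switching to compound symmetry or AR(1) while keeping the random effect would not remove the redundancy either, since that gives three parameters of rank two. Removing three code lines and three phrases and naming a fallback would cost almost nothing.

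The redundancy stands, and so does the observation that 8.10 names no alternative structure. The rest is weaker.

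- **The harm is a chain.** It needs a warning or failure, misattribution to the unstructured matrix, choice of an equal-variance structure, and unequal variances. SAS was not run. It may simply set the subject variance to zero, which is the unstructured model alone.
- **The trigger does not fit.** Section 8.10 permits a switch when the unstructured matrix is the cause. A singularity created by the random effect does not meet that condition.
- **The size is assumed.** The documents give no SD ratio, and 8.10 does not name compound symmetry.
- **The comparison with 8.11.7 is thin.** Its structures are examples to be considered, with no order or commitment. That model covers many ECG timepoints, where failure of an unstructured matrix is more likely.
- **A prescribed order would gain little.** Heterogeneous compound symmetry adds no new model at two timepoints. Homogeneous compound symmetry is the very structure whose standard errors are the worry.
- **Deletion has its own side effect.** Under a variance-components fallback, the random effect is what keeps a subject's two records correlated. Without it they would be treated as independent.

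**Conclusion.** The random subject effect is redundant, but no change to the plan follows, because removing it gains nothing. Every contrast, standard error, df and confidence interval is the same with or without it as long as the unstructured matrix is kept. This follows from the algebra and does not rest on the assumed variances; the simulated fits at 80 and 100 subjects only confirm it. A programmer can drop the term and keep the unstructured matrix and Kenward-Roger df without altering the marginal model, provided any substitute structure still carries within-subject correlation.

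The unnamed fallback in 8.10 is missing detail that an analyst can fill sensibly. The analyses are declared exploratory with no multiplicity control. Protocol section 11 specifies no primary hypothesis test, and none of the escalation or stopping criteria in protocol 9.9 uses these models. The one unverified point is how SAS reports the singular information matrix. A warning there would concern the split of the covariance, not the estimates.
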